6.0 ADVERSE EVENT REPORTING

6.1 Adverse Events

Definition: any unfavorable medical occurrence in a human subject including any abnormal sign, symptom, or disease.

Grading: the descriptions and grading scales found in the revised NCI Common Terminology Criteria for Adverse Events (CTCAE) version 4.0 will be utilized for all toxicity reporting. A copy of the CTCAE version 4.0 can be downloaded from the CTEP website.

Attribution (relatedness), Expectedness, and Seriousness: the definitions for the terms listed that should be used are those provided by the Department of Health and Human Services' Office for Human Research Protections (OHRP). A copy of this guidance can be found on OHRP's website:

<http://www.hhs.gov/ohrp/policy/advevntguid.html>

All HRPO guidelines for reporting unanticipated problems will be followed.

6.2 Measurement of Post-Operative Complications

In addition to reporting AEs according to the CTCAE (as described in Section 6.1), postoperative complications will be reported using the Clavien-Dindo Classification of Surgical Complications Appendix B. Adverse Events and Complications will be assessed from time of study intervention to the three month post visit.

The principal investigator will also determine complications based on normal standards.

Complication Examples:

1. Intra-operative complications for a RAPN include but are not limited to injury to the surrounding organs and vessels, excessive blood loss requiring blood transfusions, and conversion to radical nephrectomy or open surgery.
2. Postoperative complications for RAPN include but are not limited to urine leak, urinoma, abscess, pseudoaneurysm, ileus, blood transfusion requirements, incisional hernias, wound infection, blood transfusion requirements, deep venous thrombosis, pulmonary embolism, myocardial infarction, stroke, and death.

7.0 DATA SUBMISSION SCHEDULE

Case Report Form	Submission Schedule
Original Consent Form	Prior to registration
Eligibility Checklist	Prior to starting treatment
Baseline Data Sheet	Following receipt of pathology report
Adverse Event/Complication Assessment	Baseline, and 3 months after surgery and at the time of any complication
Follow-Up Data Sheet	3 months after surgery then annually thereafter
SAE Reporting Form	At the time of any SAE

8.0 DATA AND SAFETY MONITORING

In compliance with the Washington University Institutional Data and Safety Monitoring Plan, the Principal Investigator will provide a Data and Safety Monitoring (DSM) report to the Washington University Quality Assurance and Safety Monitoring Committee (QASMC) semi-annually beginning six months after accrual has opened (if at least five patients have been enrolled) or one year after accrual has opened (if fewer than five patients have been enrolled at the six-month mark).

The Principal Investigator will review all patient data on an ongoing basis and provide a semi- annual report to the Quality Assurance and Safety Monitoring (QASM) Committee. This report will include:

- HRPO protocol number, protocol title, Principal Investigator name, data coordinator name, regulatory coordinator name, and statistician
- Date of initial HRPO approval, date of most recent consent HRPO approval/revision, date of HRPO expiration, date of most recent QA audit, study status, and phase of study

- History of study including summary of substantive amendments; summary of accrual suspensions including start/stop dates and reason; and summary of protocol exceptions, error, or breach of confidentiality including start/stop dates and reason
- Study-wide target accrual and study-wide actual accrual
- Protocol activation date
- Average rate of accrual observed in year 1, year 2, and subsequent years
- Expected accrual end date
- Objectives of protocol with supporting data and list the number of participants who have met each objective
- Measures of efficacy
- Early stopping rules with supporting data and list the number of participants who have met the early stopping rules
- Summary of toxicities
- Abstract submissions/publications
- Summary of any recent literature that may affect the safety or ethics of the study

The study principal investigator and research patient coordinator will monitor for serious toxicities on an ongoing basis. Once the principal investigator or research patient coordinator becomes aware of a serious adverse event, the SAE will be reported to the HRPO and QASM Committee according to institutional guidelines.

9.0 STATISTICAL CONSIDERATIONS

9.1 Study Objectives and Endpoints

Primary Outcome:

Evaluation of renal function following RAPN with or without hilar clamping using:

1. Decline in estimated glomerular filtration rate (eGFR). eGFR is calculated from serum creatinine using the Chronic Kidney Disease Epidemiology Collaboration formula [11]. Decline in eGFR = Postoperative eGFR – Preoperative eGFR.
2. Decline in split renal function (SRF). SRF is a percentage of the total renal function supplied by one kidney. Ideally each kidney has a SRF of 50%. SRF is measured during renal scintigraphy (renal scan). Decline is SRF =preoperative SRF- postoperative SRF (3 month).

Secondary Outcomes:

1. Oncological outcomes:
 - a. Pathological results
 1. Pathologic margin status
 2. Tumor histology, including Fuhrman grade if applicable
 3. Distance between tumor margin and surgical margin

- b. Evidence of disease recurrence or metastasis on follow-up imaging
 - 1. Recurrence free survival
- 2. Perioperative outcomes
 - a. Estimated blood loss
 - b. Operative time and warm ischemia time
 - c. Intra-operative complications, including but not limited to injury to the surrounding organs and vessels, excessive blood loss requiring blood transfusions, and conversion to radical nephrectomy or open surgery.
 - d. Length of postoperative hospital stay
 - e. Postoperative complications, including but not limited to urine leak, urinoma, abscess, pseudoaneurysm, ileus, blood transfusion requirements, incisional hernias, wound infection, blood transfusion requirements, deep venous thrombosis, pulmonary embolism, myocardial infarction, stroke, and death.

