5.2 Operative Procedure

5.2.1. Randomization

Randomization will take place in the operating room, after feasibility of RAPN off clamp is confirmed. Patients will be randomized to either off-clamp RAPN or traditional clamped RAPN in a 1:1 ratio, for a total of 40 patients allocated to each group. To minimize selection bias, a randomization table will be developed before initiation of enrollment.

Envelopes containing randomization assignments will be created, sequentially numbered and sealed. Once enrollment is initiated, randomization envelopes will be opened for each subject after informed consent is granted and study eligibility is confirmed in the operating room.

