5.4 Postoperative Care

The postoperative management is standard of care for all patients who undergo RAPN.

Three month post op visit:

- CR/eGFR
- Renal Scan
- CT/MRI of abdomen
- Chest x-ray (CXR)

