9.2 Study Design

This is a single institution, prospective, randomized, controlled study to evaluate the off-clamp RAPN technique. Parallel group design with randomization allocation ratio of 1:1 to off-clamp RAPN technique (study treatment) and traditional clamped RAPN technique (control) will be utilized. Study will be conducted at Washington University and will enroll approximately 80 participants over the course of the study.

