APPENDIX C: Study Schedule of Events

	Pre-Operative Assessments	Surgery	Post-Operative Assessments		
	Baseline ¹	RAPN	1 day Post RAPN	3 months Post RAPN	Every 12 months ²
Informed Consent	X				
Demographics	X				
Medical & Surgical History	X				
Height & Weight	X				
Serum Creatinine/eGFR	X		X	X	X
Renal Scan	X ¹			X	
CT/MRI of abdomen	X ¹			X	X
CXR	X ¹			X	X
Incl./Excl. Criteria Confirmation	X				
Randomization		X			
Perioperative Outcomes		X			
Pathology results		X			
Adverse Event Assessment				X	
Assessment of Evidence of Disease Recurrence				X	X

¹ Scans (Renal Scan, CT/MRI of abdomen and Chest Xray (CXR)) performed prior to or at time of baseline assessments per standard of care

² From the date of 3-mo follow up for total of 3 years only for patients with malignant pathological outcome

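### The plan does not provide for masking of whoever processes the 3-month renal scan, the source of one of its two primary measures

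*Combined protocol and SAP*

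**What the plan says.** Section 9.1 lists two primary measures of renal function. One is the decline in eGFR, calculated from serum creatinine. The other is the decline in SRF, the preoperative percentage minus the 3-month percentage. On how SRF is obtained it says only "SRF is measured during renal scintigraphy (renal scan", with no reader or processing method.

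The scans are routine ones. Section 5.4 states "The postoperative management is standard of care for all patients who undergo RAPN" and lists a renal scan at the 3-month visit. The first footnote to Appendix C says the baseline scans are "performed prior to or at time of baseline assessments per standard of care".

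On allocation, 5.2.1 states "Randomization will take place in the operating room, after feasibility of RAPN off clamp is confirmed", using a table prepared in advance and sealed, numbered envelopes. This is the only bias control the protocol describes. The design statement in 9.2 reads "This is a single institution, prospective, randomized, controlled study to evaluate the off-clamp RAPN technique" and does not say whether anyone is masked.

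Among the secondary oncological outcomes, 9.1 lists "Pathologic margin status" and "Distance between tumor margin and surgical margin". Section 7.0 has the Baseline Data Sheet submitted "Following receipt of pathology report".

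**The concern.** The surgeon cannot be masked. The person who derives a percentage from a scan three months later does not need to know how the hilum was handled. The plan neither keeps that information from the reader nor says whether the reader has it.

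SRF is the measure for which this matters most. It is the kidney-specific half of the primary outcome, whereas eGFR reflects both kidneys. If processing the scan leaves room for judgement, knowledge of the arm could move the 3-month percentage in a consistent direction.

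The setting gives any expectation a direction. The trial is run at one institution, the Principal Investigator developed the off-clamp technique (1.1), the stated hypothesis favours it (1.2), and the Principal Investigator also reviews the accumulating data (8.0). The stake is a between-arm SRF difference that mixes the effect of clamping with the effect of knowing the arm.

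**Working it through.** **No figure to reproduce.** The plan states no SRF variability, expected difference, significance level or power. The only design number is 40 per group (5.2.1), and 2 × 40 = 80 agrees with 9.2. The check is therefore mainly one of reading.

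**Which reads are exposed**

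| Measure | When and how obtained | Exposed to knowledge of arm? |
|---|---|---|
| Baseline SRF | Scan before or at baseline (Appendix C), hence before randomization in the operating room (5.2.1) | No, if reported at that time |
| 3-month SRF | Standard-of-care scan after surgery (5.4) | Possibly; nothing prevents it |
| eGFR | Calculated from serum creatinine (9.1) | Very little |
| Margin status and distance | Taken here as coming from the pathology report (9.1, 7.0) | Possibly; masking may not be achievable |

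The envelopes protect the assignment until they are opened. They have no bearing on what is known when the 3-month scan is processed.

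**How a shift would act.** Let decline = preoperative SRF − 3-month SRF. Suppose knowledge of the arm moves the 3-month reading by b points, on average, in one arm only. That arm's mean decline moves by b, and so does the between-arm difference. The number of patients does not enter, so averaging over 40 does not reduce it.

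**Scale, under assumptions that are not in the documents.** Take the SD of SRF change as 5 to 10 points, b as 1 or 2 points, 40 per arm, and no true difference.

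- Standard error of the arm difference = SD × √(2/40). For SD 5 this is 5 × 0.2236 = 1.12; for SD 10 it is 10 × 0.2236 = 2.24.
- With d = b / SE, a two-sided 5% z-test rejects with probability Φ(−1.96 + d) + Φ(−1.96 − d).

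| Assumed SD | Assumed b | d | Rejection rate with no true effect |
|---|---|---|---|
| 5 | 1 | 0.89 | 14.5% |
| 5 | 2 | 1.79 | 43.2% |
| 10 | 1 | 0.45 | 7.3% |
| 10 | 2 | 0.89 | 14.5% |

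Section 9.3 specifies a descriptive analysis and no test, so the last column is only a yardstick. The bias of b points in a reported difference does not depend on whether a test is done.

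**The case against.** The strongest reply is that the plan is silent rather than wrong. It does not say who reads the scans, what the request form contains, or that anyone outside the operating room learns the arm. A reader might infer that the readers know the arm, or that the results will be biased; the documents support neither. The Principal Investigator's interest in the technique cannot simply be attributed to an unnamed scan reader. Nor does the protocol describe how SRF is processed, so the room for judgement is an assumption. All of this stands, and it limits the point to an unprotected step.

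It does not dispose of the point. Opening an envelope in the operating room does not confine the assignment to that room, and no text keeps it from later readers.

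Three other inferences go too far:

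- *That the whole primary outcome is exposed.* eGFR is little affected, and only one of the two scans comes after randomization.
- *That margin assessment is equally open to remedy.* Section 5.2.3 describes cautery around the tumor in the off-clamp technique. The clamped technique is not described in comparable detail, so the specimen itself might reveal the arm.
- *That masking is free, or that a shift could never be found later.* Masking needs altered requests and some restraint over the operative note. Nothing in the documents rules out a later masked re-read of the scans.

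**Conclusion.** The point holds for the 3-month renal scan. The plan leaves one of two primary measures open to processing with knowledge of the arm, and a small change would reduce that risk. The change should be made, but this is a precaution and not a demonstrated fault.

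The size is unknown. The documents contain no SRF variability and no evidence that any shift occurs; the 1- to 2-point shifts and the SDs of 5 to 10 points above are assumptions chosen to show scale. The conclusion also assumes that a person has some discretion in processing the scan and that baseline scans are reported before surgery. For margin status and distance the same omission exists, but masking is less certain to work, so that part is secondary.

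**What to change.** Add to 5.4 and 9.1 wording to this effect:

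*The request for the 3-month renal scan gives the operation actually performed (partial or radical nephrectomy) and the side, but not the clamping technique or the assigned arm. The existing reader processes the baseline and 3-month scans by the same method and reports SRF without consulting the operative note. These values are the trial data.*

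The request must name the operation actually performed because 5.2.2 allows conversion to radical nephrectomy in either arm; a form that always said partial nephrectomy would then be false.

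Where feasible, omit the clamping technique from the pathology request as well, and acknowledge that the specimen may still reveal it.

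The cost is low: a change to the request wording and a note to the readers, with no new reader, scan or visit. The downside is that masking fails if the reader opens the operative record.

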9.2 Study Design

This is a single institution, prospective, randomized, controlled study to evaluate the off-clamp RAPN technique. Parallel group design with randomization allocation ratio of 1:1 to off-clamp RAPN technique (study treatment) and traditional clamped RAPN technique (control) will be utilized. Study will be conducted at Washington University and will enroll approximately 80 participants over the course of the study.

9.3 Data Analysis

Data analysis for this study will be descriptive in nature. Demographic and clinical characteristics of the sample, as well as local recurrence and post-surgery complications will be summarized using descriptive statistics. Kaplan-Meier product limit method will be used to estimate the 2-year overall and disease-free survival. The median disease-free survival, overall survival and their 95% confidence interval will also be estimated.

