These preliminary results have shown comparable perioperative outcomes to traditional clamped RAPN, while mitigating renal functional damage and providing excellent oncologic control. To date, we have submitted for publication: 1) video and detailed description of our off-clamp RAPN technique, 2) safety and efficacy of this technique in our initial 42 patient experience, 3) safety and efficacy of our technique for technically difficult renal tumors, and 4) a retrospective matched cohort study comparing off-clamp to clamped RAPN. We aim to prospectively compare renal functional, perioperative and oncologic outcomes between our off-clamp technique and traditional clamped RAPN.

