1.2 Rationale

Randomizing patients to either traditional clamped RAPN or off-clamp technique will allow for prospective data in regards to the effect of hilar clamping on renal function. We hypothesize that the off-clamp RAPN technique will lead to decreased decline in renal function compared to the on-clamp RAPN.

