2.0 OBJECTIVES

2.1 Primary Objective

1. To determine if off-clamp RAPN technique better preserves long-term renal function than the traditional clamped RAPN technique.

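### Section 9.3 plans only a descriptive analysis, names neither primary outcome and specifies no between-arm estimate, so the comparative primary objective cannot be answered as written

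*Combined protocol and SAP*

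**What the plan says.** The purpose is comparative throughout the combined protocol and SAP.

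- The end of section 1.1 states: "We aim to prospectively compare renal functional, perioperative and oncologic outcomes between our off-clamp technique and traditional clamped RAPN".
- Section 1.2 gives a directional hypothesis: "We hypothesize that the off-clamp RAPN technique will lead to decreased decline in renal function compared to the on-clamp RAPN".
- The primary objective in section 2.1 is "To determine if off-clamp RAPN technique better preserves long-term renal function than the traditional clamped RAPN technique".
- Sections 5.2.1 and 9.2 describe 1:1 randomisation, 40 patients per arm, with clamped surgery as control.
- Section 9.1 introduces the primary outcome as "Evaluation of renal function following RAPN with or without hilar clamping using" two measures. The first is "Decline in eGFR = Postoperative eGFR – Preoperative eGFR", with no time point. The second is "Decline is SRF =preoperative SRF- postoperative SRF (3 month"), so SRF is fixed at 3 months.

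Section 9.3 is the only analysis text. It begins "Data analysis for this study will be descriptive in nature" and continues "Demographic and clinical characteristics of the sample, as well as local recurrence and post-surgery complications will be summarized using descriptive statistics". It then adds Kaplan-Meier estimates of overall and disease-free survival at 2 years, and median survival times with 95% confidence intervals.

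**The concern.** A randomised trial exists to estimate a difference between arms. Here the design, hypothesis and objective call for one, and the analysis section does not provide it for either primary outcome. At stake is whether the trial can answer its own question from a prespecified analysis.

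If a comparison is added later, two choices remain free when the data are in hand. One is which postoperative eGFR to use. The other is whether a patient converted during surgery counts in the arm assigned or the arm of the operation performed. Section 5.2.2 gives conversion from off-clamp to clamped surgery for excessive bleeding as an example. Grouping by operation performed would move such a patient into the clamped group, and the comparison would no longer be a randomised one.

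**Working it through.** The plan gives no calculation for the primary comparison, so there is no figure to reproduce. The check sets the text of the sections side by side.

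**1. Is either primary outcome analysed in 9.3?** Section 9.1 lists two: eGFR decline and SRF decline. Section 9.3 names demographics, clinical characteristics, local recurrence, complications, overall survival and disease-free survival. Overlap: 0 of 2.

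**2. Is any between-arm quantity specified?** Section 9.3 mentions no arm, difference, test or model. Its only confidence intervals are for median survival times. Between-arm estimates specified: 0.

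**3. Does another section fill the gap?** No. Section 9.1 defines the outcomes but gives no method. Section 9.2 gives the design and the number of patients. Section 8.0 lists measures of efficacy only as an item in the monitoring report.

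**4. How many eGFR comparisons fit the text?** Appendix C schedules postoperative creatinine/eGFR at day 1, at 3 months and every 12 months. Counting the annual visits as one option gives 3 time points. Grouping as randomised or as performed gives 2 options. That leaves 3 × 2 = 6 different eGFR comparisons, all consistent with the plan. They answer different questions. Day 1 is an immediate postoperative value, and the annual values exist only for patients with malignant pathology (section 5.5 and Appendix C, footnote 2).

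**5. Which time point covers everyone?** Section 5.5 ends follow-up at 3 months for benign pathology and continues it to 3 years for malignant pathology. Three months is therefore the last visit scheduled for all patients. It is also the time point already fixed for SRF.

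**6. Are the two declines in the same direction?** No. eGFR decline is post minus pre, while SRF decline is pre minus post. The retrospective cohort in section 1.1 reports eGFR declines as positive numbers, 4.9 off-clamp and 11.7 clamped. In that sign, off-clamp minus clamped is 4.9 − 11.7 = −6.8. Under the section 9.1 formula the same data give −4.9 − (−11.7) = +6.8. A reader needs to know which sign favours off-clamp surgery.

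**7. Does baseline adjustment matter?** Only modestly. With equal variances and baseline correlation ρ, the ratio of the ANCOVA standard error to that of an unadjusted change score is √((1+ρ)/2). At assumed values of ρ this is √(1.9/2) = 0.975 for ρ = 0.9 and √(1.6/2) = 0.894 for ρ = 0.6. The interval is about 3% to 11% narrower. The essential repair is the between-arm estimate; ANCOVA improves it a little.

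**The case against.** The best defence is that the first sentence of 9.3 covers all data analysis. Section 9.1 frames the outcome by clamping and section 9.2 specifies parallel groups, so by-arm descriptive summaries of eGFR and SRF are compatible with the plan. A descriptive analysis is also not wrong in itself. Both points stand. They do not remove the problem, because two arm summaries without a difference and its uncertainty do not determine whether one technique is better.

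Several stronger readings are tempting, but the documents do not support them:

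- *The arms will be pooled.* In 9.3 the reference to the sample attaches only to demographic and clinical characteristics. The section is silent on arms; it does not say that results are combined.
- *Renal function will not be reported at all.* Silence in 9.3 does not establish this. The secure statement is that the primary comparison is not specified.
- *Conversions will be common enough to distort the result.* Section 5.2.2 allows for conversion and gives no rate. The 1.6% conversion to radical nephrectomy in section 5.3 comes from a 450-case multi-institutional series. This trial excludes masses judged too complex for off-clamp surgery (section 3.2) and randomises only after feasibility is confirmed in the operating room (section 5.2.1). Its own rate is unknown.
- *Eighty patients are too few.* The plan states no power, effect size or standard deviation, and section 1.1 gives neither the test nor the time point behind the earlier cohort's p-value. The sample size cannot be called wrong on this evidence.

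**Conclusion.** The point holds. The objective, hypothesis and randomised design are comparative, while the only analysis text is descriptive, names 0 of 2 primary outcomes and gives 0 between-arm estimates. As written, the plan cannot answer section 2.1, even on the generous reading that both outcomes would be tabulated by arm. The eGFR time point and the analysis group of converted patients are also unspecified, and both can change the result.

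The conclusion rests on the wording alone. It needs no assumption about effect size, variability or conversion rate, and it does not say how far any result would move. It should be corrected before the data are analysed.

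**What to change.** Replace the first sentence of 9.3 with a primary analysis along these lines:

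1. Estimate the off-clamp minus clamped difference, with 95% confidence interval, in 3-month eGFR and in 3-month SRF of the operated kidney. Use ANCOVA with the corresponding baseline value as covariate. An unadjusted difference in change would also repair the defect.
2. Analyse all patients in their randomised group, regardless of intraoperative conversion.
3. As a sensitivity analysis, report results with and without patients converted to radical nephrectomy.
4. State that 3 months is used because it is the last visit scheduled for all patients and matches the SRF definition. Report annual eGFR in patients with malignant pathology as supportive, and reconcile the long-term wording of 2.1 with this.
5. Use one sign direction for both declines in 9.1.

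Wording on missing 3-month values and on handling two primary outcomes would be useful further detail, but the repair does not depend on it.

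If only description is intended, the alternative is to reword 1.2 and 2.1 accordingly and still report both outcomes by arm. That gives up the stated hypothesis.

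The cost is text changes and a little more analysis work. Baseline and 3-month creatinine and renal scans are already in Appendix C, so no visits or patients are added. The real downside is a primary claim limited to 3 months, a change of scope that the sponsor must decide. The documents do not give the trial's status; if outcome data have already been seen, the added analysis should be labelled post hoc.

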5.5 Duration of Follow-Up

The follow up management is standard of care but uniquely different for patients based on pathologic outcome. Patients with a malignant (cancerous) surgical pathology will be followed for a period of 3 years. Patients with a benign (non-cancerous) surgical pathology will only be followed through a period of 3 months postoperatively. Patients removed from

this study for unacceptable adverse events will be followed until resolution or stabilization of the adverse event.

Yearly follow up visits:

- CR/eGFR
- CT/MRI of abdomen
- Chest x-ray (CXR)

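### Does the lack of a scheduled scan between months 15 and 27 undermine the 2-year disease-free survival estimate in section 9.3?

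*Combined protocol and SAP*

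**What the plan says.** Section 9.3 declares the analysis descriptive and states that the "Kaplan-Meier product limit method will be used to estimate the 2-year overall and disease-free survival". It gives no time origin, no rule for dating a recurrence, no visit window, and no statement on whether deaths count as events. Section 9.1 names recurrence free survival, not disease-free survival, and ties it to "Evidence of disease recurrence or metastasis on follow-up imaging".

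The scan schedule is in Appendix C. The row "Assessment of Evidence of Disease Recurrence" is marked at 3 months and then every 12 months, as are the abdominal CT/MRI and the chest film. Footnote 2 sets the anchor and the population for the yearly column: "From the date of 3-mo follow up for total of 3 years only for patients with malignant pathological outcome". The follow-up data sheet in section 7.0 is consistent with this: "3 months after surgery then annually thereafter".

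Section 5.5 is looser. It says "Patients with a malignant (cancerous) surgical pathology will be followed for a period of 3 years" and lists "Yearly follow up visits" with no starting point. For benign pathology it says "Patients with a benign (non-cancerous) surgical pathology will only be followed through a period of 3 months postoperatively", so those patients are not at risk at 24 months.

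**The concern.** Read literally, Appendix C puts the recurrence assessments at about months 3, 15 and 27 after surgery. The landmark in 9.3 falls in the long gap between the last two. A Kaplan-Meier curve for a scan-detected event drops only where scans take place. With recurrence dated at the detecting scan, the value read at month 24 is therefore the value reached at month 15, and a figure labelled 2-year leaves out recurrences that arise after month 15 and are first seen at month 27. With recurrence dated at the midpoint between scans, those found at month 27 move to month 21 and all of them count.

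The same data could thus give two figures, and the confidence interval would not show the difference. Section 2.2 sets equivalence of oncologic outcomes as a secondary objective, so an optimistic figure, or a rule chosen after the data are seen, would be unwelcome.

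**Working it through.** The plan states no disease-free survival rate, so there is no figure of its own to reproduce. The size has to be shown over assumed rates.

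**Inputs from the documents.** Landmark 24 months (9.3). Scans at months 3, 15 and 27 (Appendix C, footnote 2). About 80 patients, 40 per arm (5.2.1, 9.2). Benign cases leave at 3 months (5.5).

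**Assumptions.** True 2-year rate S(24) of 98, 95 or 90%. Constant hazard, so S(t) = S(24)^(t/24). Clock from surgery. Malignant share 60 to 100%, which gives 48 to 80 patients pooled and 24 to 40 per arm.

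**1. Dated at the detecting scan, every event scan-detected.** The month-24 reading equals S(15). At 95%: 0.95^(15/24) = 96.85%, an excess of 1.8 points (1.845 before rounding). At 98%: 98.75%, an excess of 0.7. At 90%: 93.63%, an excess of 3.6.

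**2. Half of the events dated exactly** (deaths, for instance). The reading is S(24)^0.5 × S(15)^0.5. At 95% this is √(0.95 × 0.9685) = 95.92%, an excess of 0.9. At 98% and 90% the excess is 0.4 and 1.8. If half of the recurrences come to light between visits, the result is about the same.

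**3. Midpoint dating.** (15 + 27)/2 = 21, which is before 24, so the reading equals S(27) = 0.95^(27/24) = 94.39%, a shift of −0.6. At 98% and 90% the shift is −0.2 and −1.2. A simulation of four million event times at 95% gave +1.85 for step 1 and −0.63 for this step.

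**4. Other readings of the schedule.** If the yearly visits in 5.5 run from surgery (12, 24, 36 months), or if disease-free survival is itself counted from the 3-month visit, a scan falls at month 24 and the shift is zero when scans are on time. If half of those scans come late, the excess at 95% is 0.5 × (S(12) − S(24)) = 0.5 × (97.47 − 95.00) = 1.2 points.

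**5. Against sampling error.** At 70% malignant, 0.70 × 80 = 56 patients. The step 1 excess is 0.01845 × 56 = 1.03 patients at 95%, and 0.4 and 2.0 patients at 98% and 90%. The binomial standard error at 95% is √(0.95 × 0.05/56) = 2.9 points. The Wilson 95% interval at 95% is 87.8 to 98.0% with 80 patients and 84.9 to 98.5% with 48, so 10 to 14 points wide. For one arm it is 83.5 to 98.6% with 40 and 78.6 to 99.0% with 24, so 15 to 20 points wide.

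**6. What the alternatives would give.** Reading just after the 27-month scan gives S(27), 94.4% at the assumed 95%: a correct 27-month figure, but no longer a 2-year one. Interpolating between the two scans gives 96.85 − (9/12) × (96.85 − 94.39) = 95.0%, close to the truth under a constant hazard, but for about 0.05 × 56 = 2.8 expected events.

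**The case for a change.** The strongest argument for a change is that the gap is real, the rule is missing, and a sentence would supply it. The shift is systematic, so a confidence interval does not cover it. Sharing a schedule does not remove it entirely either: it cancels between arms only when their rates are equal. If one arm stood at 95% and the other at 90%, the month-24 readings would be 96.85% and 93.63%, so a true gap of 5.0 points would show as 3.2.

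The facts in that argument stand. Its weight does not. The contrast between 96.8% and 94.4% sets ordinary detection dating against a midpoint rule that no section suggests, while 9.1 describes recurrence as seen on imaging. With detection dating, the estimate is a well-defined time to detected recurrence, and its only limitation is that scans are a year apart, as with any annually imaged outcome. The loss of 1.8 points in the two-arm example is small beside intervals 15 to 20 points wide per arm. No test, margin or decision rule in 9.3 depends on it.

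The substantive remedies each carry a cost. A 27-month landmark would no longer match the 2-year overall survival figure reported beside it. An interval-censored estimator is a less familiar method, with its own interpolation assumption, for about three events. Statisticians could reasonably prefer any of the three.

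**Conclusion.** No change to the plan is needed. Appendix C and 7.0 do leave month 24 between scans, and 9.3 does not say how recurrence is dated. This is missing detail that an analyst fills in the usual way: clock from surgery, recurrence dated at first detection, and the handling of deaths stated with the result. The differing names in 9.1 and 9.3 and the unanchored visits in 5.5 are drafting looseness of the same kind.

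On that convention the 2-year figure is too high by 0.7, 1.8 or 3.6 points at an assumed 98, 95 or 90%. This rests on a constant hazard and on every event being found at a scheduled scan. It falls to about half if half of the events are dated otherwise, and to zero if scans fall on time at month 24 of the clock used. A hazard concentrated between months 15 and 24 would enlarge it. Across the assumed rates it comes to between 0.4 and 2.0 patients of 56. Overall survival is unaffected by scan timing. A reader of the results should bear in mind that, under Appendix C, the last scheduled scan before the landmark is at month 15.
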